**1. Purpose and Objectives:**

This protocol does not include any administration of medication or other interventions. This protocol will record cognitive performance and decision-making behavior in Veterans who seek mental health services in the substance use disorder intensive outpatient program (IOP). The goal is to identify the neurobehavioral effects of a structured, brief cognitive-based psychotherapy currently being conducted in the IOP along with other supportive, unstructured, treatments. The benefit of this study will be to obtain a better understanding of neurobehavioral changes occurring from evidence-informed treatments.

Aim 1: To determine if measurable neurobehavioral function in the domains of problem solving, decision making, and motoric impulsivity is predictive of treatment success and adherence outcomes (e.g. Urinary Drug Screen/Breathalyzer Analysis results, appointment no shows, early drop out, recidivism).

Exploratory Aim: To determine if there are between group differences in neurobehavioral function as a result of treatment modality being received as standard of care in the substance use outpatient setting.

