**2. Background, Significance, and Scientific Rationale:**

It is established that impulsivity is a tremendous risk factor for the development of addiction (Bickel et al., 2007) and for treatment failure (Loree, Lundahl, & Ledgerwood, 2015). Impulsivity is a multi-faceted trait that has been conceptually divided into a more decision-based domain and rapid “acting without thinking” motoric domain(Swann, [name], Moeller, & Dougherty, 2002), where greater impulsivity in both domains has been found in patients addicted to stimulants in particular (Ahn & Vassileva, 2016). Trait personality measures of impulsivity typically capture some elements of both domains and frequently correlate poorly with individual task metrics of impulsivity. Therefore, comprehensive assessment of cognitive change (as it may underlie improvements in mental perseverance and thus changes in substance use) should include objective behavioral measures of both decision-making and motoric impulsivity. The addition of focused neurocognitive tasks holds potential to *identify mechanisms of* psychotherapy effects, such as whether a structured cognitive behavioral therapy may reduce substance use by promoting mindful attention generally, or whether it influences future-orientation specifically.

There are currently multiple treatments being conducted in the IOP clinic as standard of care, with a particular psychotherapy of interest for this study being a brief, structured cognitive-based treatment, called the Mind Freedom Plan (MFP). This treatment is one of two treatments being administered, with the other being a supportive, unstructured treatment that is also provided as standard of care. The aim of the MFP treatment is to improve problem solving abilities, increase engagement in pleasurable activities, and teach the patient to identify and change maladaptive thoughts. Structured worksheets for each session have been developed for

the purpose of achieving these goals. An exploratory aim of the current study will be to identify whether there are neurobehavioral differences in subjects as a result of the treatment modality being conducted during their treatment regimen. This is novel due to the lack of studies previously examining neurobehavioral impulsivity tasks as a metric for exploring differences in treatment modality.

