The VA has an increasing need for brief, efficacious interventions to assist Veterans in reducing alcohol and substance abuse. The emphasis on brief therapies is partly due to VA initiatives and ongoing access concerns that have limited the number of sessions providers are allotted with patients. Additionally, there are significant efforts to roll out and integrate evidence based practices across the VA. This exploratory aim will be an effort to meet the intersection of these demands by examining a brief evidence-informed therapy for substance users in outpatient treatment. The focus of this aim will be to determine whether this treatment results in measurable changes in neurobehavioral performance shown to be aberrant in addiction. These behaviors might serve as *early-indicator proxy markers* for improvement in cognitive domains relevant to addiction, which could in turn result in longer-term benefits of alcohol or drug abstinence.

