Day -7 – Day -1	
 
- Contact with potential subjects for recruitment during a face to face meeting when they are in the SATP clinic
 
- Consent and pre-treatment baseline assessment
 
	Brief Addiction Monitor (BAM), Barrett Impulsivity Scale-11 (BIS-11), Posttraumatic Checklist-5 (PCL-5), Beck's Anxiety Inventory
Day 0 – Day 28	
 
- Participants engage in either MFP or TAU treatment during their IOP engagement
 
	N/A
Day 29 – Day 35	
 
- Post-treatment assessment
 
- Chart review: treatment engagement (appointment no shows, early drop out) and Breathalyzer/UDS results, results of Beck Depression Inventory and Quality of Life Inventory.
 
	BIS-11, Delay Discounting Task, Stop-Signal Task, Emotional Go-NoGo task, Quality of Life Inventory
Day 120	
 
- Chart Review: recidivism (treatment re-entry) and Breathalyzer/UDS results
 
	N/A

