#### Data Analysis

The analytic plan includes conducting an independent-group t-test of each of the following continuous dependent variables, or chi-square for categorical dependent variables: 1)

proportion drug-free urines; 2) retention in program (Chi-Square); 3) Quality of life score on the QOLI; 4) Delay discounting constant k; 5) Stop signal reaction time (SSRT) on the stop-signal task; 7) Reaction time in the Emotional Go-NoGo task, 8) errors in the DKEFS Tower Test.

A repeated-measures design will be used to examine the within-subjects effects of the treatments on state depression and quality of life, as well as for a group X treatment interaction effect. Although we do not expect an intervention of this time scale of to alter trait impulsivity, we will also analyze within-subject changes in BIS11 scores as an exploratory analysis. Lastly, a between-group design comparing the MFP group vs. TAU group for substance use primary outcomes of symptomology and neurobehavioral measures for problem solving and impulsivity. Individual differences in PTSD and anxiety measures and other symptomatology will be included as covariates to account for confounding factors in the analyses.

c. Facilities and Resources

The consent procedures and behavioral testing of this protocol will take place in the new second-floor Mental Health services facility at RICVAMC. Written informed consent procedures and clinical interviewing will take place in private interview rooms of this new second-floor RICVAMC wing. Questionnaires and laboratory behavioral tasks will be administered at dedicated research task workstations installed in testing rooms.

d. Staff Qualifications

*[name].* will be the Principal Investigator of this protocol. [name] has a 5/8 VA appointment and a joint (faculty) appointment as Associate Professor of Psychiatry at Virginia Commonwealth University. He has extensive experience in the laboratory testing of impulse control and decision-making in addicted inpatients, outpatients, and at-risk human subjects. He is also known for his successful design and execution of protocols to examine the neurocircuitry of motivation and self-control in addicted and adolescent at-risk populations. He has over 50 peer-reviewed publications and book chapters, 48 of which are available in PUBMED.

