## **7. Recruitment:**

Recruitment: This project will recruit Veterans enrolled in the Substance Abuse Intensive Outpatient Program (IOP). The IOP includes five different groups over three days of the week for four weeks. Veterans are also randomly assigned to meet with a provider for four weekly individual sessions. Currently, Veterans either meet with one of two providers to complete the Mind Freedom Plan treatment, or they meet with a different provider to receive supportive, unstructured, therapy.

For the study, Veterans will be identified in their medical chart as being enrolled in IOP following the clinic intake and prior to beginning treatment. Research staff will contact Veterans face to face when they present to the SATP clinic to provide information about the study and explore if they are interested in participating. If they express interest, staff will schedule an appointment to meet with the potential participant to introduce the study, review and sign consent, and complete the baseline assessment self-report measure before they begin treatment.

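### Aim 1's covariate list omits the assigned therapy, so part of a task–outcome association could reflect the MFP/TAU contrast; the bias is small unless therapy effects are large

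*Protocol*

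**What the plan says.** - **Aim 1** (Protocol section 1) asks whether neurobehavioral function "is predictive of treatment success and adherence outcomes", such as drug-screen and breathalyzer results, no-shows, drop-out and recidivism. It does not separate Veterans by therapy.
- **Two therapies.** The project timeline in section 4.b states for Day 0 to Day 28: "Participants engage in either MFP or TAU treatment during their IOP engagement". Section 7 states how Veterans reach one or the other: "Veterans are also randomly assigned to meet with a provider for four weekly individual sessions". Two providers deliver MFP and a different one delivers supportive therapy. The allocation ratio is not given.
- **Timing of the predictors.** The timeline lists for Day 29 to Day 35: "BIS-11, Delay Discounting Task, Stop-Signal Task, Emotional Go-NoGo task, Quality of Life Inventory". Sections 4.a and 4.b likewise place the desktop tasks, and section 4.b the Tower Test, in the second visit. There is no baseline score on any of these tasks. The BIS-11, a questionnaire, is given at both visits.
- **Possible effects of therapy.** Section 2 gives the focus of the exploratory aim as to "determine whether this treatment results in measurable changes in neurobehavioral performance shown to be aberrant in addiction". It also raises "whether a structured cognitive behavioral therapy may reduce substance use by promoting mindful attention generally". Section 5 says the study could establish that the brief intervention is effective for substance use disorders.
- **Adjustment.** The Data Analysis section states: "Individual differences in PTSD and anxiety measures and other symptomatology will be included as covariates to account for confounding factors in the analyses". Therapy appears as the factor in the MFP versus TAU comparison, and perhaps in the repeated-measures analysis of depression and quality of life ("as well as for a group X treatment interaction effect"). Neither is an analysis of task score against an Aim 1 outcome.

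**The concern.** On the protocol's own reasoning, the therapy a Veteran receives may change the task score measured after it and may also change substance use or attendance. Therapy would then be a possible common cause of the Aim 1 predictor and the Aim 1 outcome. The symptom measures named for confounding are person-level characteristics and do not stand in for it.

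If both effects exist, and the effect on outcome does not run wholly through the task score, then Veterans on one therapy will tend to differ from the others on both variables. That alone produces a correlation across the whole sample, even if task performance says nothing about outcome among Veterans on the same therapy. If the two effects run in opposite directions, the induced correlation is negative and could hide a real positive one. A reader of the Aim 1 result could not tell these cases apart from prediction by impulsivity or problem solving.

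**Working it through.** The protocol gives no effect size, standard deviation, power or alpha, so there is no planned figure to reproduce. The check sizes the bias under stated assumptions.

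**Inputs**
- n = 35 (section 3, approximate).
- Share on MFP, p: not stated. Both 1:1 (p = 1/2) and 2:1 (p = 2/3) are tried. The latter is what equal assignment across three providers would give.
- Therapy effect on task score and on outcome: not stated. Assumed equal at d within-therapy standard deviations on each, from 0.2 to 1.0.
- No association between task score and outcome within either therapy.
- Two-sided alpha of 0.05 (assumed).

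**Formula.** Write v = p(1 − p). With effects a on the task score and b on the outcome, the correlation induced across the whole sample is

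r = v·a·b / √[(1 + v·a²)(1 + v·b²)],

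which for a = b = d becomes r = v·d² / (1 + v·d²).

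**Numbers**
- 1:1, v = 1/4. At d = 0.5: 0.0625/1.0625 = 0.059. At d = 0.8: 0.16/1.16 = 0.138. At d = 1.0: 0.25/1.25 = 0.200.
- 2:1, v = 2/9. At d = 0.5: 0.0556/1.0556 = 0.053. At d = 0.8: 0.1422/1.1422 = 0.125. At d = 1.0: 0.2222/1.2222 = 0.182.

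**False-positive rate.** 20,000 simulated trials per setting with n = 35, testing the correlation without and with therapy in the model:

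| d on both | r, 1:1 | Rate without therapy, 1:1 | r, 2:1 | Rate without therapy, 2:1 | Rate with therapy, either split |
|---|---|---|---|---|---|
| 0.2 | 0.010 | 4.9% | 0.009 | 4.9% | 4.8–5.0% |
| 0.5 | 0.059 | 6.2% | 0.053 | 6.1% | 5.1% |
| 0.8 | 0.138 | 12.8% | 0.125 | 11.2% | 4.9–5.0% |
| 1.0 | 0.200 | 20.9% | 0.182 | 18.7% | 5.0% |

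With therapy in the model the mean partial correlation stays within 0.002 of zero in every setting. The smallest correlation that reaches significance at n = 35 is 0.33, so even the largest induced value would not usually be significant on its own.

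**When the bias vanishes.** It is zero if MFP has no effect on the task score or none on the outcome. It is also zero if MFP affects the outcome only through the task score: the score is then a mediator, and the therapy contrast is part of the genuine link. Including therapy still gives a valid task–outcome slope in that case.

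**The case against.** The strongest reply is that the protocol contains no Aim 1 model to criticize. The Data Analysis section lists t-tests and chi-square tests without defining their groups, a repeated-measures analysis, and the MFP versus TAU comparison. The covariate sentence directly follows that comparison, where therapy is already the factor, and nothing says the list is closed. This stands in part. A reader might infer that the protocol prescribes a pooled, unadjusted Aim 1 analysis, but it does not say so. Pooling is inferred from the wording of Aim 1 and the absence of any split. Still, the sentence speaks of the analyses generally and names what is to handle confounding, and therapy is not there.

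Second, Aim 1 is about prediction, not cause, and section 2 hopes the behaviors will act as proxy markers whose improvement leads to later abstinence. On that reading the unadjusted association is a legitimate target. This also stands, and is a reason to report both associations rather than replace one with the other.

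Third, both groups attend the same intensive program and differ only in four weekly individual sessions, so effects of 0.8 to 1.0 standard deviations on both variables have no support in the document. That is fair, and it limits the size of the point.

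Two other replies fail. Random assignment to provider balances the Veterans between therapies but does not stop therapy from moving both variables afterward. The statement that no change in trait impulsivity is expected concerns the BIS-11, not the tasks.

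**Conclusion.** The point holds as a modest, inexpensive improvement. Assigned therapy is a possible common cause of the post-treatment task scores and the Aim 1 outcomes, and the covariates named for confounding do not include it. Under equal assumed effects the spurious correlation is about 0.05 to 0.06 at d = 0.5, with a false-positive rate near 6%. It reaches 0.18 to 0.20, with a rate of about 19% to 21%, only at d = 1.0 on both variables.

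Two stronger readings are not supported. One is that Aim 1 would in effect be answered by the therapy contrast: that would need large effects on both variables, which the protocol neither states nor implies. The other is that bias is present whenever MFP affects both variables: it also needs a route from MFP to the outcome that bypasses the task score. Such routes are plausible, since section 2 says MFP also works on pleasurable activities and maladaptive thoughts, but the protocol does not establish them.

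**What to change.** Add to the Data Analysis section that each Aim 1 association between a task score and an outcome is estimated in a regression model, linear or logistic according to the outcome, that includes assigned modality (MFP or TAU) along with the symptom covariates. State that the unadjusted association and the association within each arm are reported descriptively beside it. A regression has to be named because the listed t-tests and chi-square tests cannot carry a covariate.

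The cost is one degree of freedom (from 33 to 32 in the simplest model at n = 35) and no new data, because modality is already needed for the exploratory aim. In logistic models with few events the extra term weighs more, and the within-arm estimates will be imprecise.

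This does not address the separate problem that the tasks are given on Day 29 to Day 35, after the no-shows, drop-out and drug-screen results of the treatment period have accrued.

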**5. Risk/Benefit Assessment:**

The procedures proposed herein are limited to computerized psychological tasks and symptomatology questionnaires. This protocol is considered to be minimal risk.

Risks:

*5.a. Psychological distress due to performance of cognitive tasks or completion of questionnaire instruments on depression and PTSD.*

There is a small possibility that a subject may feel uncomfortable in endorsing symptoms of depression, PTSD, or anxiety. In addition, subjects may perceive lack of self-efficacy or cognitive skill when performing the desktop computerized tasks.

*Risk mitigation steps:* Research staff are trained to be encouraging of the subjects and their efforts, and to not comment negatively on performance, other than the automatically-generated "please try harder" feedback of the CEDT, which is required to help ensure that the subject tries his/her best.

Either the study PI or a designated mental health clinician from the suicide response team of the Mental Health Service Line will be on the Richmond VAMC campus while the participants are completing the questionnaires and assessments. The research staff will have updated contact information available for the PI, designated mental health clinician (if different that day from the PI), the Richmond VAMC Urgent Care Clinic (aka, SOS Clinic), and the Veterans Suicide Hotline (aka Veterans Crisis Line, [name]).

Upon obtaining written informed consent, we will also provide subjects with resource materials for mental health services and contact numbers for suicide prevention should their symptoms become acute at any point during/after the protocol.

*5.b. Disclosure of sensitive information*

There is a small possibility of an unauthorized party gaining access to sensitive research-collected information in conjunction with personally-identifiable information (PII) or protected health information (PHI) contained in the CPRS database.

*Risk mitigation steps:* This risk is mitigated by secure information-technology (IT) procedures (see “Data Safety Monitoring” below) for CPRS, coupled with the sequestration of PII/PHI from research data by using anonymous subject ID numbers assigned by this protocol. The document that enables linkage of research data (protocol ID number) with PII is not electronic, and is kept physically secured.

Benefits:

There are no medical benefits for participation in this protocol.

Risk/Benefit Assessment: This protocol is minimal risk. The investigative team contends that the benefits of this study in terms of generalizable neurobehavioral and psychiatric knowledge outweigh the risks to subjects.

Importance of knowledge to be expected: It is important to understand the effect of treatments being conducted in clinical settings here at McGuire VA Medical Center. This study has the opportunity to establish that a brief cognitive-based intervention is effective in treating patients with substance use disorders. Additionally, this study can expand our understanding of neurobehavioral effects of treatment on impulsivity and substance use outcomes.

Subject Compensation:

All subject compensation will come in the form of a direct deposit payment issued by the McGuire VAMC. The original grant funding source for this study was the Durham VA Mental Illness, Research, Education, and Clinical Center (MIRECC). These funds have been transferred to the McGuire VA Medical Center, and will be paid to participants directly from the VA. Subjects who consent to participate in the current study will be compensated \$20.00 for the first meeting (approximately 60-90 minutes), and \$30.00 for the second meeting (90 minutes).

## **6. Data Safety and Monitoring:**

Data Sharing

This protocol will not create a data repository and is not a multi-site study. It is not anticipated that data will be shared with an entity outside of this facility. If this is to occur, IRB approval will be sought and any shared data will be completely de-identified, per VA regulation (1605.1 Appendix B).

**Data-Safety Monitoring Plan (DSMP):**

DSMP Element 1: Handling of Unexpected or Adverse Events

Veteran participants will only be scheduled for testing during business hours, when a clinician of the suicide response team is always on call at RICVAMC. Should a participant express suicide ideation, the research assistant will first call or page the PI ([name]) to notify him, then will summon the SOS Crisis Team that is operated by the Mental Health Service, where responders will include an MSW or clinical psychologist to further evaluate the subject. As a backup, the research team will contact the RICVAMC Suicide Prevention Coordinator, and/or a study staff member will escort the participant to the RICVAMC emergency department and wait with the participant until assessed by a mental health clinician. Following the intervention and complete disposition of the subject, the research staff member and Clinicians will fully document the incident.

If the subject does not agree to undergo clinical evaluation, and the (SOS Crisis Team clinician meeting with the subject determines that it is appropriate to initiate the civil-commitment process consistent with state law, the clinician and/or the research staff member may initiate direct contact

with the subject's family members, friends, local magistrate, and/or local law-enforcement authorities in order to assure appropriate evaluation and treatment. Information collected as part of this clinical evaluation will become part of the subject's mental-health record. Thus, the identified clinician will communicate details of the intervention to the subject's outpatient mental-health-care provider or primary-care provider, as appropriate, to assure safety and continuity of clinical care.

With respect to after-hours suicidal or other psychiatric reactions in outpatients or community subjects that do not take place during testing at RICVAMC, subjects will have been provided with both a VA suicide hotline information card, as well as a copy of the signed consent form, on which after-hours numbers for the PI ([name]) are available. Should a subject call with a mental health crisis, they will be referred to the national VA suicide hotline, and a member of the research team will notify clinical staff at RICVAMC as appropriate, and will follow up with the subject.

For all adverse events, the IRB will be notified in writing by the PI within five days with all the details of the incident.

